9.3.1 Efficacy estimands

The following 4 attributes describe the estimands (International Council for Harmonisation [ICH] Addendum, 2019) that will be used to define the treatment effect of interest for the co-primary endpoints of study participant-level outcomes:

PASI90 response at Week 16:

1. Treatment: 320mg bimekizumab Q4W for 16 weeks.
2. Target Population: adult Korean study participants meeting the protocol-specified inclusion/exclusion criteria.
3. Intercurrent event handling: An intercurrent event is defined as discontinuation of IMP prior to Week 16. A composite strategy will be implemented in which a positive clinical outcome is defined as achieving PASI90 response at Week 16 and not discontinuing IMP through Week 16.
4. Study participant-level summary measure: Odds ratio comparing bimekizumab to placebo.

Any missing data not associated with discontinuation of IMP will also be imputed as a nonresponse.

IGA 0/1 (clear or almost clear with at least a 2-category improvement from Baseline) response at Week 16:

1. Treatment: 320mg bimekizumab Q4W for 16 weeks.

2. Target Population: adult Korean study participants meeting the protocol-specified inclusion/exclusion criteria.
3. Intercurrent event handling: An intercurrent event is defined as discontinuation of IMP prior to Week 16. A composite strategy will be implemented in which a positive clinical outcome is defined as achieving IGA 0/1 response at Week 16 and not discontinuing IMP through Week 16.
4. Study participant-level summary measure: Odds ratio comparing bimekizumab to placebo.

Any missing data not associated with discontinuation of IMP will also be imputed as a nonresponse.

The secondary efficacy binary endpoints (PASI100 response at Week 16, IGA 0 response at Week 16, PASI75 response at Week 4, PSD [P-SIM] [itch, pain, and scaling] response at Week 16, Scalp IGA 0/1 response at Week 16, and DLQI Total Score 0/1 response at Week 16) will have the same estimand structure as for the primary estimands.

The following 4 attributes describe the estimand (ICH Addendum, 2019) that will be used to define the treatment effect of interest for the secondary efficacy endpoint percentage change from Baseline in BSA affected by PSO Week 16:

1. Target population: Study participants meeting the protocol-defined inclusion/exclusion criteria.
2. Study participant-level outcome: Percentage change from Baseline in BSA affected by PSO at Week 16

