9.3.2 Analysis of the primary efficacy/primary endpoint

The co-primary efficacy variables for this study will be PASI90 response and IGA 0/1 response at Week 16.

The primary analyses for these endpoints will be produced on the RS. In addition, sensitivity analyses for the co-primary endpoints will be produced on the FAS and PPS. Observed case summaries (excluding subjects with missing PASI/IGA data at Week 16) will also be provided.

Estimands related to primary efficacy analyses are described in Section 9.3.1.

An intercurrent event is defined as discontinuation of IMP prior to Week 16. A composite strategy will be implemented in which a positive clinical outcome is defined as achieving the primary endpoint (PASI90 or IGA 0/1) at Week 16 and not discontinuing IMP prior to Week 16.

The justification of this approach is that discontinuation of IMP for any reason is considered to be indicative of an ineffective response to the IMP. Therefore, a successful primary outcome depends both on achieving the response (PASI90 or IGA 0/1) and continuing study treatment through 16 weeks.

A study participant will be classified as a PASI90 responder if the PASI score at Week 16 has improved at least 90% from Baseline and the study participant has not discontinued IMP prior to Week 16.

A study participant will be classified as a IGA 0/1 responder if the IGA score at Week 16 is 0 or 1 (clear or almost clear) with at least a 2-category improvement from Baseline in the IGA score and the study participant has not discontinued IMP prior to Week 16.

The evaluation of superiority (bimekizumab vs placebo treatment comparison) will be based on the Cochran-Mantel-Haenszel (CMH) test. Odds ratios and 95% confidence intervals (CIs) based on the CMH method will also be presented.

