9.3.3 Secondary efficacy endpoint analyses

The secondary efficacy variables will be analyzed for all study participants in the RS.

No formal statistical testing will be conducted for the secondary efficacy variables. Nominal p-values for the bimekizumab vs placebo treatment comparison will be described in the SAP.

The secondary efficacy endpoints will be derived as follows:

- PASI100 responder at Week 16: PASI score at Week 16 has improved by 100% from Baseline and the study participant has not discontinued IMP prior to Week 16.
- IGA 0 responder at Week 16: IGA score at Week 16 is 0 (Clear) with at least a 2-category improvement from Baseline in the IGA score and the study participant has not discontinued IMP prior to Week 16.
- PASI75 responder at Week 4: PASI score at Week 4 has improved by $\geq 75\%$ from Baseline and the study participant has not discontinued IMP prior to Week 4.
- PSD (P-SIM) itch responder at Week 16: Itch score has improved (decreased) by ≥ 4 points from Baseline to Week 16 (using weekly averages) and the study participant has not discontinued IMP prior to Week 16. This will be assessed only in study participants with a Baseline itch score ≥ 4 .
- PSD (P-SIM) pain responder at Week 16: Pain score has improved (decreased) by ≥ 4 points from Baseline to Week 16 (using weekly averages) and the study participant has not discontinued IMP prior to Week 16. This will be assessed only in study participants with a Baseline pain score ≥ 4 .
- PSD (P-SIM) scaling responder at Week 16: Scaling score has improved (decreased) by ≥ 4 points from Baseline to Week 16 (using weekly averages) and the study participant has not discontinued IMP prior to Week 16. This will be assessed only in study participants with a Baseline scaling score ≥ 4 .
- Scalp IGA 0/1 responder at Week 16 for study participants with scalp involvement at Baseline: Scalp IGA score at Week 16 is 0/1 (clear or almost clear) with at least a 2-category

improvement from Baseline in the IGA score and the study participant has not discontinued IMP prior to Week 16. Only study participants with a Scalp IGA score ≥ 2 at Baseline will be included.

- DLQI Total Score 0/1 at Week 16: DLQI Total score is equal to 0 or 1 at Week 16 and the study participant has not discontinued IMP prior to Week 16.

For the binary secondary efficacy endpoints assessing the superiority of bimekizumab vs placebo, the estimand structure as specified for the primary analysis will be implemented.

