Derived variables in general will display the mean, SD and median to 1 more decimal place than the variables used in the derivation. If the number of decimal places reported in the raw data is varied then use either the maximum raw number of reported decimal places or 3, whichever is the lowest, as a guide for the descriptive statistics.

Statistical tests of efficacy variables will be presented as two-sided p-values rounded to three decimal places. P-values less than 0.001 will be presented as "<0.001" and p-values greater than 0.999 will be presented as ">0.999."

Per protocol, visit windows of ± 3 days from the first dose (W0) to the Week 16 visit are permissible; for SFU Visit, permissible window is ± 7 days from last dose + 20 weeks. For byvisit presentations, data from unscheduled visits should generally not be included. If the data of unscheduled visit is the only record prior to first IMP administration, it will be an exception and treated as baseline value. In case of repeated laboratory tests at a particular visit, the last measurement should generally be used for visit presentation in by-visit summaries.

In cases where vendor data is assigned to an unscheduled visit instead of a scheduled visit, the assessments will be mapped into the scheduled visit if the assessment dates fall into the permissible window, as detailed above.

A complete set of data listings containing all documented data and all calculated data (eg, change from Baseline) will be generated.

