5.1.1.7 Handling of dropouts or missing data

Details about approaches to handle missing data are described in this section.

Efficacy missing data 5.1.1.7.4

An intercurrent event is defined as discontinuation of IMP prior to Week 16.

For study participants who experience an intercurrent event, the intercurrent event date is defined as:

Last study treatment date + 28 days (dosing interval) + 3 days (visit window)

For both co-primary endpoints (PASI90 and IGA 0/1 at Week 16), participants with an intercurrent event will be considered as nonresponder.

For secondary efficacy binary endpoints (PASI100 response at Week 16, IGA 0 response at Week 16, PSD [P-SIM] [itch, pain, and scaling] response at Week 16, Scalp IGA 0/1 response at Week 16, and DLQI 0/1 response at Week 16), study participants with intercurrent event will be handled using the same approach as the co-primary endpoints.

For PASI75 response at Week 4, a study participant will be considered a nonresponder only if the intercurrent event date occurs prior to the date of the Week 4 assessment.

Any missing data for the primary and secondary binary endpoints not associated with discontinuation of IMP will also be imputed as a nonresponse.

For the secondary continuous endpoint (percent change from baseline in BSA affected by PSO), participants with an intercurrent event are treated as though they had completed the randomized study treatment through Week 16 by imputing data following an intercurrent event using LOCF (see section 5.4.1.2.2). In addition, missing data not associated with discontinuation of IMP will also be imputed using LOCF.

For all tertiary endpoints, all data collected after an intercurrent event will be treated as missing and subject to imputation as described in section 5.5.

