5.4.1.2 Main analytical approach

5.4.1.2.1 **Binary endpoints**

The binary secondary efficacy endpoints include:

- PASI100 response at Week 16,
- IGA 0 response at Week 16,
- PASI75 response at Week 4,
- PSD [P-SIM] [itch, pain, and scaling] response at Week 16,
- Scalp IGA 0/1 response at Week 16,
- DLOI 0/1 response at Week 16

o authorization Viereot These secondary endpoints will have the same estimand structure as for the co-primary endpoints, which is defined as follows:

- Treatment: Bimekizumab 320mg Q4W for 16 weeks
- Target Population: adult Korean study participants meeting the protocol-specified inclusion/exclusion criteria
- Intercurrent event handling: •
 - PASI100 response at Week 16, IGA 0 response at Week 16, PSD [P-SIM] [itch, pain, and scaling] response at Week 16, Scalp IGA0/1 response at Week 16, DLQI 0/1 response at Week 16

An intercurrent event is defined as discontinuation of IMP prior to Week 16. A composite strategy will be implemented in which a positive clinical outcome is defined as achieving response at Week 16 and not discontinuing IMP through Week 16. Study participants with intercurrent event of discontinuation of IMP prior to Week 16 will be considered nonresponders (i.e. negative clinical outcome).

PASI75 response at Week 4

An intercurrent event is defined as discontinuation of IMP prior to Week 4. A composite strategy will be implemented in which a positive clinical outcome is defined as achieving response at Week 4 and not discontinuing IMP through Week 4. Study participants with intercurrent event of discontinuation of IMP prior to Week 4 will be considered nonresponders (i.e. negative clinical outcome).

Population level summary: odds ratio comparing bimekizumab to placebo

In the above scenario, missing data at the time point of interest that are not preceded by an intercurrent event, as well as any data after an intercurrent event, will be imputed as non-responders. While this approach is described as a composite strategy for intercurrent event handling, it is equivalent to applying non-responder imputation (NRI).

The number and percentages of PASI100, IGA 0, PSD [itch, pain, and scaling] responders, Scalp IGA, DLQI 0/1 responders at Week 16 and PASI75 responder at Week 4 will be reported for each treatment group.

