#### Treatment Compliance 6.1.10

Study treatment compliance will be calculated and summarized for the SS.

Treatment compliance will be calculated as:

(Actual number of completed injections/Expected number of injections)  $\times$  100

In this study, Baseline visit and Weeks 4, 8, 12 are dosing visits. For study participants who complete all injections as planned, the expected number of injections is 8. For participants who permanently discontinue treatment, the number of expected injections is based on the time of early discontinuation relative to the dosing visits.

Bimekizumab

Compliance will be summarized descriptively by treatment group and overall. The number and percentage of study participants meeting certain compliance thresholds (<75% and  $\geq 75\%$ ) will also be reported.

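### For Week 4 PASI75, the SAP's last dose + 31 days event date lets some participants who stopped IMP before Week 4 count as responders, contrary to protocol 9.3.3 (minor)

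*SAP*

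**What the plan says.** **Protocol.** Section 9.3.3 defines a Week 4 PASI75 responder by at least 75% improvement from Baseline, with the further condition that "the study participant has not discontinued IMP prior to Week 4". Section 9.3.1 says the binary secondary endpoints "will have the same estimand structure as for the primary estimands". Section 9.3.2 justifies that structure on the ground that "discontinuation of IMP for any reason is considered to be indicative of an ineffective response to the IMP".

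**SAP 5.1.1.7 (Efficacy missing data).** The intercurrent event date is "Last study treatment date + 28 days (dosing interval) + 3 days (visit window"). For Week 4 PASI75 the rule is that "a study participant will be considered a nonresponder only if the intercurrent event date occurs prior to the date of the Week 4 assessment". A missing value not linked to discontinuation is also nonresponse.

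**SAP 5.4.1.2.1 (Binary endpoints).** For PASI75 at Week 4, participants with an "intercurrent event of discontinuation of IMP prior to Week 4 will be considered nonresponders". The 31-day date is not mentioned there.

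**SAP 5.1.1.1.4 (mapping of early discontinuation visits).** A PEOT held after a scheduled visit is assigned to the next scheduled visit and treated as observed there. A PEOT held at a scheduled visit belongs to that visit.

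**SAP 6.2 (Appendix 2).** The only declared change from the protocol is LOCF in place of multiple imputation, for BSA and PHQ-9.

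**The concern.** The endpoint is a composite: the participant must reach the PASI threshold and must not have stopped IMP before Week 4. The second condition matters only when a Week 4 PASI value exists, because a missing value is already nonresponse. For someone who stops early, that value comes from a PEOT visit mapped to Week 4 or held at the Week 4 visit. Those are the cases that the 31-day date fails to catch.

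The threshold can be reached in such a participant, since protocol 4.3 reports PASI75 responses after one bimekizumab dose. Read plainly, SAP 5.1.1.7 and SAP 5.4.1.2.1 then tell a programmer to classify the same person differently. In a 45-participant trial that choice should be fixed before unblinding.

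**Working it through.** The plan gives no figure for this endpoint, so there is none to reproduce. The check is date arithmetic, followed by an illustration of size. Days are counted from the Baseline dose (day 0).

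**Inputs**
- Event date: last dose + 28 + 3 (SAP 5.1.1.7).
- Dosing: "In this study, Baseline visit and Weeks 4, 8, 12 are dosing visits" (SAP 6.1.10), so Baseline is the only dose due before Week 4.
- Visit window: SAP 5.1 states that windows of ±3 "days from the first dose (W0) to the Week 16 visit are permissible".
- PASI is scheduled at Weeks 1, 2 and 4 (protocol Table 1-1), so a PEOT after the Week 2 visit maps to Week 4.

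**Dates for a participant dosed only at Baseline**
- Event date = 0 + 28 + 3 = day 31.
- Week 4 window = 28 ± 3 = days 25 to 31.
- Week 2 window = 14 ± 3 = days 11 to 17, so a PEOT mapped to Week 4 can fall from day 12.
- Nonresponder test: 31 < assessment day. It is met on 0 of the 20 days from 12 to 31. The first day that meets it is 32.

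**Two cases, each with PASI improved by at least 75%**

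| Case | SAP 5.1.1.7 | Protocol 9.3.3 |
|---|---|---|
| Stops on day 20, PEOT on day 20 mapped to Week 4 | 31 is not before 20: responder | nonresponder |
| Stops on day 20, PEOT at the Week 4 visit on day 28 | 31 is not before 28: responder | nonresponder |

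With less than 75% improvement the participant is a nonresponder under every rule. A PEOT before the Week 2 visit maps to Week 1 or 2, which leaves Week 4 missing and so also nonresponse.

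**Later visits.** The by-visit responder summaries in SAP 5.5.1 use the same event. With a last dose on day 28, the event date is 28 + 31 = day 59, and the Week 8 window is 56 ± 3 = days 53 to 59. Again no in-window day is later than the event date. If the Week 4 dose was early, on day 25, the event date is day 56 and days 57 to 59 would be caught.

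**Size.** One reclassified participant moves the rate by 1/30 = 3.3 points on bimekizumab or 1/15 = 6.7 points on placebo. The documents give no Week 4 rates. I assumed 15 to 27 of 30 responders on bimekizumab and 0 or 1 of 15 on placebo, and removed one bimekizumab responder. The least favourable results are at 15/30:

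| Bimekizumab v placebo | CMH p | Fisher p | OR |
|---|---|---|---|
| 15/30 v 1/15 | 0.005 | 0.007 | (15 × 14)/(15 × 1) = 14.0 |
| 14/30 v 1/15 | 0.008 | 0.008 | (14 × 14)/(16 × 1) = 12.25 |
| 15/30 v 0/15 | not used | 0.0006 | not calculated |
| 14/30 v 0/15 | not used | 0.0014 | not calculated |

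SAP 5.4.1.2.1 switches to Fisher's exact test, without an odds ratio, when an arm has zero or very low response. At 0/15 Fisher therefore applies. At 1/15 either test might, because very low is not defined.

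**The case against.** The strongest defence is that the protocol gives no calendar definition of discontinuation and leaves detail to the SAP. Last dose + 28 + 3 is a coherent operational definition under four-weekly dosing, since a participant dosed at Baseline is covered until the Week 4 dose is missed. SAP 5.4.1.2.1 refers to an intercurrent event, the term that 5.1.1.7 dates, so the two SAP sections can be read as consistent. An operational definition need not be listed as a change.

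Much of this stands. A reader might infer a deliberate rewriting of the protocol endpoint; the documents do not show that. The defence still fails for a participant with a PEOT at about day 20. That visit records that IMP was stopped before Week 4, and the 31-day date does not capture it. Under the defence's own reading, the discontinuation condition has no effect at an in-window Week 4 visit, and protocol 9.3.3 remains unimplemented.

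A reader might also infer that the rule never operates. It does from day 32, so it reaches late Week 4 visits, and protocol 7.2 and section 8 anticipate pandemic disruption to visits.

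Materiality is fairly challenged too. A result changes only if the participant stops before Week 4, has a PASI value that counts as Week 4, and has improved by at least 75%. The endpoint carries a nominal p-value only, and the observed-case sensitivity analysis in SAP 5.4.1.3 sets those who stopped prematurely to missing.

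**Conclusion.** Wrong as written, and minor. The SAP's Week 4 rule can count as a responder someone whom protocol 9.3.3 defines as a nonresponder, and Appendix 2 does not mention it. The date arithmetic is exact given the stated windows and dosing visits.

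The effect is 3.3 or 6.7 points per affected participant. The number affected cannot be estimated from the documents and may be zero. Within the assumed Week 4 rates, reclassifying one bimekizumab responder leaves the nominal p at about 0.008 or less under either test, so the estimate moves but the conclusion does not.

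The documents do not support extending this to the co-primary endpoints: SAP 5.1.1.7 makes any participant with an intercurrent event a Week 16 nonresponder, with no comparison of dates.

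**What to change.** In SAP 5.1.1.7, replace the Week 4 sentence with: *For PASI75 at Week 4, a participant recorded as having permanently discontinued IMP before the Week 4 visit, including one whose Week 4 value is a mapped PEOT assessment, is a nonresponder.*

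Date discontinuation by the recorded IMP discontinuation date, which SAP 5.5.3 already relies on without defining. If none is recorded, use the PEOT date. Do not use the last dose date: a participant who attends Week 4 and only then stops would otherwise be classed as having stopped earlier.

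Apply the same rule to the by-visit responder summaries and figures in SAP 5.4.1.2.1 and 5.5.1 at Weeks 4, 8 and 12. Changing only the secondary endpoint could give two different Week 4 PASI75 rates in one report.

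If the sponsor prefers to keep the 31-day date, state it in 5.4.1.2.1 and declare it in Appendix 2 as a departure from protocol 9.3.3.

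The cost is one replaced sentence, one date definition and a cross-reference in each of the two sections, or one sentence and one Appendix 2 entry if the date is kept. No new analysis is needed. The eCRF is not among the documents, so whether it holds a discontinuation date is an assumption; the PEOT date is the fallback.

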5.1.1.7.2 PK missing data

Pharmacokinetic analyses will be based on observed data; no data will be imputed. If plasma concentration measurements are below the lower limit of quantification (LLOQ), then for calculation of the derived statistics the result will be set to half of the LLOQ.

5.1.1.7.3 Incomplete dates and times

Partial dates may be imputed for the following reasons:

- Classification of AEs as treatment-emergent
- Classification of medications as prior or concomitant

Imputed dates will not be shown in the listings; all dates will be displayed as reported in the database.

The following rules will be applied for partial start dates and time:

- If only the month and year are specified and the month and year of the first dose of IMP is not the same as the month and year of the start date, then use the 1st of the month, or the date of Screening if this is later (if the latter imputation results in an end date that is earlier than the start date, then use the 1st of the month).
- If only the month and year are specified and the month and year of the first dose of IMP is the same as the month and year of the start date, then use the date of the first dose of IMP. If this results in an imputed start date that is after the specified end date, then use the 1st of the month, or the date of Screening if this is later (if the latter imputation results in an end date that is earlier than the start date, then use the 1st of the month).
- If only the year is specified, and the year of the first dose of IMP is not the same as the year of the start date then January 01 will be used.
- If only the year is specified, and the year of the first dose of IMP is the same as the year of the start date, then the date of the first dose of IMP will be used. If this results in an imputed start date that is after the specified end date, then January 01, or the date of screening if this is later will be used (if the latter imputation results in an end date that is earlier than the start date, then January 01 will be used).

If the start date is completely unknown, then use the date of dosing. If this results in an imputed start date that is after the specified end date, then use January 01 of the year of the end date, or the date of Screening if this is later. orization

The following rules will be applied for partial stop dates:

- If only the month and year are specified, then use the last day of the month •
- If only the year is specified, then use December 31 of the known year •
- If the stop date is completely unknown, do not impute the stop date •

5.2 **Participant Dispositions**

The number of study participants screened and screen failures and the primary reason for screen failure are summarized for all participants screened.

The number and percentage of study participants who completed or prematurely discontinued the treatment period, as well as the reason for discontinuation will be summarized based on the RS. The number of study participants who completed the SFU and the number of study participants who enter the MAP will also be summarized.

The number and percentage of study participants who discontinued due to AEs will be separately summarized based on the RS.

The disposition of study participants for all study participants screened will include the number of study participants included in each analysis set (RS, SS, FAS, PPS, CFS and PK-PPS) overall.

The following listings will be presented:

- Study participants who did not meet study eligibility criteria (ES)
- Study participants disposition (ES)
- Study discontinuation (RS
- Visit dates (RS)
- Study participants analysis sets (RS)
- Rescreened Subjects (ES) _

